5.4. Patient Population

The following patient populations described in [Table GBGC.5.1](#) will be used to analyze the data.

Table GBGC.5.1. Analysis Populations for Study H9X-MC-GBGC

Population	Definition
All Entered	All patients who signed an informed consent
All Randomized	All patients who were randomized to a treatment arm as planned
Nonrandomized	All patients who entered, but were not randomized to a treatment arm
ITT	All randomized patients who took at least 1 dose of the study medication for an assigned treatment arm. For EMA, patients treated with diet and exercise alone who have not previously received metformin will be excluded from the ITT population for the primary analysis related to the primary endpoint (HbA1c) change from baseline to Week 26.
PP	All ITT population patients who have met the following criteria: 
 • Have no important protocol deviations (Section 5.7) expected to influence the assessment of the primary objective • Have an overall compliance of at least 75% up to Week 26 • Have completed the double-blinded period (26 weeks therapy [Visit 9]) with nonmissing HbA1c for both the Week 26 and baseline visits
HO	A subset of the ITT population who signed an informed consent for the HO addendum and completed testing on at least 1 occasion.

Abbreviations: EMA = European Medicines Agency; HbA1c = hemoglobin A1c; HO = health outcomes;

ITT = intent-to-treat; PP = per protocol.

5.5. Patient Disposition

Patient discontinuations will be listed and summarized for all randomized patients. The number and percentages of all patients who completed or discontinued from the study will be summarized for each treatment group from baseline to Week 26, from baseline to Week 52.

For the randomized population, discontinuations due to an AE or death, and discontinuations from study medication will be summarized separately for each treatment group.

The p-value to test the overall treatment effect and the p-value to compare the difference between All Dula and placebo across all reasons of discontinuation will be presented.

In addition, all entered patients will be summarized including, but not limited to, the total number of patients screened (entered), the number of patients excluded, the total number of patients randomized, the number of patients who entered into the double-blinded period, and the

number of patients who entered into the open-label period for each treatment group. Within each treatment group, the number of patients randomized but not treated, the number of patients included in the ITT population, the number of patients who completed 26 weeks of therapy, the number of patients who completed 52 weeks of therapy, the number of patients who completed safety follow-up (V801), and the number of patients discontinued will be summarized. Treatment difference will be compared using Fisher's exact test.

5.6. Patient Characteristics

Demographic and baseline clinical measures, including baseline Tanner stage by sex, will be summarized as described in Section 5.2 by each treatment group for the ITT and health outcome (HO) populations. For continuous measures, treatment differences will be analyzed using an ANOVA model with treatment as a fixed effect. For categorical measures, the overall treatment difference and between All Dula and placebo will be compared using Fisher's exact test. For either categorical or continuous measures, the p-value to test the overall treatment effect and the p-value to compare the difference between All Dula and placebo will be presented for each parameter of interest.

5.7. Important Protocol Deviations

Important protocol deviations will be listed for all randomized patients and summarized by treatment group. The rationale for choosing the important protocol deviations was based on their potential to impact the primary endpoint. The complete important protocol deviation list will be captured in an excel file, and then be converted in study data tabulation model (SDTM) as a source in addition to other necessary domains to define PP population. The decision and rationale for not reporting certain protocol deviations as important ones will be documented in the electronic trial master file (eTMF). The following protocol conditions will result in exclusion from the PP population:

- Informed consent was never obtained.
- Patients were randomized but the informed consent date is missing.
- Age <10 or age ≥ 18 years old at randomization.
- Patients have known type 1 diabetes.
- Patients have a history of diabetic ketoacidosis after receiving antidiabetes medication.
- Patients have diabetes-associated autoantibodies (GAD65 or IA2), historically or at screening.
- Patients have a hemoglobinopathy or other disorder that interferes with the accurate determination of the primary endpoint, including, but not limited to, patients with the following hemoglobin variants: HbS, HbC, HbE, HbSC, and elevated HbF.

- Patients are taking a class of antihyperglycemic medication other than biguanides (metformin) and/or basal insulin during the first 26 weeks of the trial or have stopped these medications less than 3 months before Visit 1. These antihyperglycemic medications include but are not limited to a sulfonylurea, alpha-glucosidase inhibitor, DPP-IV inhibitor, GLP-1 RA, thiazolidinedione (TZD), glinide, and sodium-glucose co-transporter 2 (SGLT-2) inhibitor.
- Patients are taking prescription weight loss medication(s) chronically during the first 26 weeks of the trial or within 30 days of screening. These medications include, but are not limited to, the following: Contrave® (naltrexone/bupropion), Saxenda® (liraglutide), Xenical® (orlistat), Meridia® (sibutramine), Acutrim® (phenylpropanolamine), Sanorex® (mazindol), Adipex® (phentermine), BELVIQ® (lorcaserin), Qsymia™ (phentermine/topiramate combination), or similar over-the-counter medications (e.g., alli®).
- Patients have an HbA1c $\leq 6.5\%$ or $>11\%$ if treated with antiglycemic medication; or $>9\%$ if treated with lifestyle only at Visit 1.
- Patients have a missing HbA1c at baseline (Visit 2) or at 26 weeks (Visit 9).
- Patients do not have an overall compliance with study drug of at least 75% up to 26 weeks.
- Patients that use systemic glucocorticoids for more than 14 days.

A complete list of important protocol deviations will be generated.

5.8. Concomitant Medications

Concomitant medications, including previous therapy for diabetes, will be summarized by different categories of medications and treatment groups using the ITT population. All concomitant therapies that were originally mapped using the World Health Organization (WHO) DRUG dictionary in the clinical trial database will be further classified using Anatomic-Therapeutic-Chemical (ATC) codes for reporting purposes.

Other prespecified concomitant medications of interest, including, but not limited to, antihypertensives, lipid lowering agents, and other cardiovascular agents; antidepressants and other psychiatric medications; antibiotics and other anti-infective therapies and other medications to treat the complications of diabetes will be summarized by treatment at baseline (Visit 2).

The number of patients and percentage of patients who took antihyperglycemic medication (nonrescued, and rescued) during the study will be summarized from Visit 1 to Visit 9 and from Visit 10 to Visit 16. Use of short-term (up to 2 weeks) of unlimited insulin therapy with continuation of study drug will not constitute rescue.

The p-value to test the overall treatment effect and the p-value to compare the difference between All Dula and placebo will be presented for each summary table.

The incidence of patients requiring rescue for severe, persistent hyperglycemia will be summarized in details in Section 5.15.5.

5.9. Study Drug Compliance

Study drug compliance will be listed and summarized for the ITT population. Patients with study drug change (dose change, study drug discontinuation) will be listed for all randomized patients.

A patient will be considered compliant for a period of interest if he or she is taking at least 75% of the expected doses for that period.

Overall treatment compliance from baseline to Week 26, and from baseline to Week 52 for each patient will be defined as taking at least 75% of the study drug for each period. The overall compliance in percentage for each patient will be calculated by taking the number of injections actually taken during that period divided by the total number of prescribed injections for this patient *100.

The p-value to test the overall treatment effect and the p-value to compare the difference between All Dula and placebo will be presented in a summary table.

The overall compliance defined as taking at least 75% prescribed medication from baseline to Week 26 will be used as one of the factors when determining if a patient is eligible for the PP population.

Overdosed subjects will be listed if those data are available.

5.10. Treatment Exposure

Treatment exposure is defined as the time from when the patient took his or her first dose until the last dosing date.

If that first dosing date is missing, it will be replaced with the randomized date. If the last dosing date is missing, it will be replaced with the date the patient discontinued treatment or completed the treatment period, whichever is earlier.

The duration of treatment exposure will be listed and summarized by each treatment group for the ITT population. The difference in exposure among treatment groups from baseline to Week 26, from Week 26 to Week 52, and from baseline to Week 52 will be compared using an ANOVA model with treatment as a fixed effect. The p-value to compare the overall treatment effect and the p-value to compare All Dula and placebo will be presented.

5.11. Primary Efficacy Endpoint Analyses

The primary efficacy measurement in this study is change in HbA1c from baseline to 26 weeks, as determined by the central laboratory.

5.11.1. Primary Analysis

Two primary estimands will be formed to compare the effect between All Dula and Placebo at Week 26. Each estimand will be tested with 2-sided alpha=0.05. The 2 estimands are derived from the ITT population for the primary efficacy endpoint:

1. Efficacy estimand from ITT population by censoring the post-rescue data
2. Treatment regimen estimand from ITT population regardless of rescue status or treatment adherence

The efficacy estimand measures the benefit of the assigned study treatment in the absence of the confounding effects of additional or alternative antihyperglycemic agents and regardless of compliance with study treatment. All scheduled post-first-dose-visit measurements up to Week 26 (Visit 9) inclusive will be used. The MMRM model mentioned in Section 5.2 will be fitted by replacing the baseline HbA1c strata with the baseline HbA1c as a covariate.

This method is chosen as the primary analysis as it is recommended by the National Research Council report (NRC 2010). This primary analysis is under missing at random (MAR) assumption and such an assumption often makes sense for the primary analysis (Little et al. 2012). Censoring the postrescue data minimizes the confounding rescue therapy's effect on the studied drug (O'Neill and Temple 2012).

The treatment regimen estimand measures the benefit of the assigned study treatment regardless of the use of any additional or alternative antihyperglycemic agents or compliance with study treatment. An ANCOVA model will be applied as the primary analysis to the complete data using multiple imputation (Section 5.11.3).

- Primary estimand for the FDA: treatment regimen estimand that will include post-rescue data
- Primary estimand for EMA: efficacy estimand excluding post-rescue data, and those patients treated with diet and exercise only who are metformin naïve from ITT population
- In general, for all other audiences: efficacy estimand that will not include post-rescue data (i.e., will censor the nonmissing, post-rescue data).

5.11.2. Sensitivity Analyses

The MMRM model mentioned in Section 5.11.1 may be applied using the efficacy estimand by replacing the fixed effect of the assigned treatment with the actual received treatment (i.e., those patients switched from the 1.5 mg dose to the 0.75 mg dose due to tolerability will be changed to the 0.75 mg group). The patients who switched from 1.5 mg to 0.75 mg will be listed.

5.11.3. Multiple Imputation for Missing Data

For the treatment regimen estimand, multiple imputation using the washout method which can be thought of as a modified placebo-based pattern mixture model (PMM) with a missing not at random (MNAR) assumption will be performed (NRC 2010; Permutt 2016). An ANCOVA with missing endpoints imputed using the washout method will be conducted. With the washout method, missing data from both treatment arms will be imputed using the data from those

patients in the placebo arm who had the measurement for the primary endpoint. Missing data from the dulaglutide arms will be imputed using only baseline and primary endpoint data from the placebo arm and none of the intermediate data observed in the placebo or dulaglutide arms. Missing data from the placebo arm will be imputed using both the baseline and all intermediate postbaseline and primary endpoint data in the placebo group. The aforementioned washout approach for missing data imputation will be implemented using SAS PROC MI and MIANALYZE. The ANCOVA model includes baseline HbA1c as a covariate, stratification factors, and treatment as fixed effects.

5.12. Key Secondary Efficacy Endpoint Analyses

The key secondary efficacy endpoints include change from baseline to Week 26 in HbA1c (each arm separately); the percentage of patients reaching a HbA1c target of <7% by Week 26; change from baseline to Week 26 for BMI and change from baseline to Week 26 for FBG.

5.12.1. Primary Analysis with Graphical Approach

The primary population for the key secondary efficacy analyses is the ITT population. Both the treatment regimen estimand and the efficacy estimand will be assessed using the same graphical testing scheme described in Section 5.3. Each set will use the overall 2-sided alpha of 0.05 to control overall Type 1 error rate after the primary objective has been achieved. The primary analysis is for the treatment regimen estimand for FDA, efficacy estimand by removing all metformin naïve patients for EMA, and efficacy estimand for all other regulatory agencies and disclosures. The same scheme will be adopted for each estimand, and each will be tested at the full significance level of 0.05. The graphical testing scheme is listed in Section 5.3.

All raw p-values generated from the following statistical models for the comparisons between All Dula or each dulaglutide dose and placebo at Week 26 will be used as the input data in the aforementioned graphical approach.

Change in HbA1c for each Dula arm (no pooling) and Placebo will be analyzed with the same model as defined in Section 5.11.1.

For the efficacy estimand, the MMRM model mentioned in Section 5.2 will be applied to change from baseline in BMI and FBG.

A longitudinal logistic regression model will be fitted to evaluate the proportion of patients achieving an HbA1c <7.0% at Week 26 using the same terms as described for the primary endpoint analysis by making these changes: adding logit as a link function in PROC GLIMMIX.

For the treatment regimen estimand, an ANCOVA model will be fitted to the complete data for change from baseline in BMI and FBG. This model includes stratification factors and treatment as fixed effects, and the corresponding baseline measure as a covariate. The missing data will be imputed (Section 5.11.3). A logistic regression model will be fitted to the complete data to analyze the proportions of patients reaching HbA1c target <7.0%. Stratification factors (insulin usage [yes, no], metformin usage [yes, no]) will be included as fixed effects, and baseline HbA1c as a covariate. Missing data at the endpoint will be imputed as not achieving the target.

5.12.2. Sensitivity Analyses

A logistic regression as a sensitivity analysis will be used to test the proportion of patients reaching HbA1c target of <7.0% at Week 26 in the ITT population by removing visit and visit-by-treatment interaction terms from the corresponding longitudinal logistic regression model described in Section 5.12.1. The patients who have been rescued or have missing data at Week 26 will be considered (imputed) as not having achieved the target.

5.13. Other Secondary Efficacy Analyses

The ITT population without postrescue therapy data (efficacy estimand) with all postfirst-dosing scheduled visits up to Week 52 (Visit 16) will be used for other secondary efficacy analyses.

These secondary endpoints include change from baseline to Week 52 in HbA1c; change from baseline to Week 52 in BMI and FBG; and the proportion of patients reaching HbA1c target of <7.0% at Week 52.

Each endpoint will be summarized by treatment group (Placebo/Dula 0.75, Dula 0.75, Dula 1.5, and All Dula) at each postdose visit. No inferential statistics will be generated. Within each treatment group, Week 26 and 52 corresponding responses will be provided using the corresponding statistical model described in Sections 5.12 and 5.11.1, respectively.

5.14. Pharmacokinetic/Pharmacodynamic Analyses

All PK/PD analyses will be performed by Lilly or its designee and documented in a separate analysis plan.

5.15. Safety Analyses

The safety parameters will include deaths, AEs, TEAEs, SAEs, AEs of special interest (AESI; which include pancreatitis, thyroid C-cell hyperplasia and C-cell neoplasms, and allergic/hypersensitivity reactions), hypoglycemic episodes, vital signs, ECG parameters, laboratory analytes including immunogenicity and hormones, and pubertal progression.

Unless otherwise stated, the ITT population will be used for analyses of the safety measurements and the all randomized population for data listings.

5.15.1. Adverse Events

An AE will be coded using the Medical Dictionary for Regulatory Activities (MedDRA). Unless otherwise specified, AEs will be reported using the MedDRA system organ class (SOC) and preferred term (PT).

Summary statistics will be provided for the following: medical history including preexisting conditions, deaths, AEs, TEAEs, SAEs, AESIs, and study discontinuations due to death or AEs from baseline to Week 26 and from baseline to Week 52. The number of patients and proportions of patients experiencing the AEs will be reported for each treatment group, and Fisher's exact tests will be used to compare the treatment groups.

Treatment-emergent AEs are defined as events that are newly reported after the first dosing or reported to worsen in severity from the first dosing. If the first dosing date is missing, the randomized date will be used to impute the first dosing date for TEAE determination. The incidence of patients with at least 1 TEAE will be reported, and the proportion of patients experiencing each reported TEAE will be presented by PT, SOC, and treatment group. The proportion of patients experiencing each reported TEAE that are assessed as possibly related to the study treatment will also be summarized (see details in Section 5.2). Additionally, a summary of TEAEs by maximum severity will be presented descriptively by treatment group.

A listing of patients discontinuing the study due to AE or death will be generated.

5.15.2. Adverse Event of Interest

5.15.2.1. Hypoglycemia

Hypoglycemia will be classified as follows (ADA 2005; IHSG 2017):

- **Documented Symptomatic Hypoglycemia**: any time a patient feels that he or she is experiencing symptoms and/or signs associated with hypoglycemia, and has a plasma glucose (PG) level of <70 mg/dL (3.9 mmol/L) or PG <54 mg/dL (3 mmol/L). Therefore, the categories of interest will be as follows:
 - Documented Symptomatic Hypoglycemia with PG <70 mg/dL
 - Documented Symptomatic Hypoglycemia with PG <54 mg/dL
- **Asymptomatic Hypoglycemia**: an event not accompanied by typical symptoms of hypoglycemia, but with measured plasma glucose of <70 or <54 mg/dL. Therefore, the categories of interest will be as follows:
 - Asymptomatic Hypoglycemia with PG <70 mg/dL
 - Asymptomatic Hypoglycemia with PG <54 mg/dL
- **Probable Symptomatic Hypoglycemia**: an event during which symptoms of hypoglycemia are not accompanied by a PG determination (but that was presumably caused by a PG concentration of <70 or <54 mg/dL).
- **Severe Hypoglycemia**: an episode requiring the assistance of another person to actively administer carbohydrate, glucagon, or other resuscitative actions. These episodes may be associated with sufficient neuroglycopenia to induce seizures or coma. Plasma glucose measurements may not be available during such an event, but neurological recovery attributable to the restoration of PG to normal is considered sufficient evidence that the event was induced by a low PG concentration.
- **Relative Hypoglycemia**: defined as symptomatic events during which the person reports any of the typical symptoms of hypoglycemia, and interprets those as indicative of hypoglycemia, but with a measured PG concentration of >70 mg/dL (3.9 mmol/L).

- Nocturnal Hypoglycemia: any hypoglycemic event that occurs between bedtime and waking. Therefore, the categories of interest will be as follows:
 - Nocturnal Hypoglycemia with PG <70 mg/dL
 - Nocturnal Hypoglycemia with PG <54 mg/dL

Total hypoglycemia includes any event that meets criteria for documented symptomatic, severe, asymptomatic, probable, or unspecified (i.e., missing symptoms or signs, but with a PG <70 or <54 mg/dL) whether day-time or nocturnal. Those categories that are defined by PG will be analyzed by the PG <70 and <54 mg/dL thresholds separately. Cases of relative hypoglycemia will also be collected but will not be included in the category of total hypoglycemia.

Therefore, the total hypoglycemia category will have the following 2 subcategories:

1. Total Hypoglycemia (events with PG <70 mg/dL included)
2. Total Hypoglycemia (events with PG <54 mg/dL included)

The ITT population without postrescue data will be used as the population for the primary analysis for hypoglycemia.

Incidence and rates for documented symptomatic, severe, and total hypoglycemia will be summarized for a 1-year (365-day) period.

Additionally, a separate analysis will report all hypoglycemia events with PG <54 mg/dL, regardless of symptoms, and all severe hypoglycemia episodes for the ITT population, including events that occurred after patients started rescue therapy. The incidence of hypoglycemic episodes will be summarized for each treatment group for 0 to 26 weeks, 26 to 52 weeks, and 0 to 52 weeks. The summary includes the number of patients and percent of patients reporting hypoglycemic episodes for a given treatment at a certain visit interval. Fisher's exact test will be used for treatment comparison.

The rate for each category of the abovementioned hypoglycemia (PG <70 and PG <54 mg/dL if applicable) in episodes/patient/year for 0 to 26 weeks, 26 to 52 weeks, and 0 to 52 weeks will be analyzed using a negative binomial model via PROC GLIMMIX with log link function. The response is the frequency of each category of hypoglycemia of interest. The model will include stratification factors, treatment, and the interaction term of treatment by baseline insulin use as fixed effects. The logarithm of days between visits will be adjusted as an offset to account for possible unequal duration between visits and between patients. The predicted hypoglycemia rate per 1-year by treatment and visit interval will also be presented. The results will also be reported for each of the subgroups of baseline insulin use (yes, no).

The stratified Wilcoxon rank sum test will be applied for treatment comparison for all postdose intervals of interest. It will only be conducted and used as the primary analysis if the negative binomial regression analysis fails to converge.

Hypoglycemic episodes that occurred while patients are on/off insulin therapy will be summarized for the 3 categories of total hypoglycemia, documented symptomatic hypoglycemia,

and any hypoglycemia with PG <54 mg/dL with or without symptoms. A hypoglycemic event is considered to have occurred on insulin therapy if the event occurred within 24 hours after insulin use. Descriptive statistics for each treatment group will include the number of patients with events, the number of events, the total person years of exposure, and the number of events per 1000-person years of exposure. For each of the 3 categories of hypoglycemia, the proportions of patients with events while on insulin therapy as well as while not on insulin therapy will be calculated out of the total number of patients with events.

A listing of the individual hypoglycemic episodes will be presented using the all randomized population.

Additional exploratory analyses may be performed if deemed necessary.

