10.4.1.2. Adverse Events of Interest

10.4.1.2.1. Hypoglycemia

Patients and their parents or legal guardians will be trained about signs and symptoms of hypoglycemia, how to treat hypoglycemia, and how to collect appropriate information in the study diary according to the Study Schedule ([Attachment 1](#)).

Hypoglycemia will be classified as follows (the plasma glucose [PG] values in this section refer to values determined by a laboratory or International Federation of Clinical Chemistry and Laboratory Medicine plasma-equivalent glucose meters and strips) (ADA 2005, 2020):

- Documented symptomatic hypoglycemia is defined as any time a patient feels that he/she is experiencing symptoms and/or signs associated with hypoglycemia, and has a PG level of <70 mg/dL (<3.9 mmol/L).
- Asymptomatic hypoglycemia is defined as an event not accompanied by typical symptoms of hypoglycemia but with a measured PG of <70 mg/dL (<3.9 mmol/L).
- Probable symptomatic hypoglycemia is defined as an event during which symptoms of hypoglycemia are not accompanied by a PG determination (but that was presumably caused by a PG concentration of <70 mg/dL [<3.9 mmol/L]).
- Severe hypoglycemia is defined as an episode requiring the assistance of another person to actively administer carbohydrate, glucagon, or other resuscitative actions. These episodes may be associated with sufficient neuroglycopenia to induce seizure or coma. Plasma glucose measurements may not be available during such an event, but neurological recovery attributable to the restoration of PG to normal is considered sufficient evidence that the event was induced by a low PG concentration.
- Nocturnal hypoglycemia is defined as any hypoglycemic event that occurs between bedtime and waking.

Cases of relative hypoglycemia, defined as symptomatic events during which the person reports any of the typical symptoms of hypoglycemia and interprets those as indicative of hypoglycemia, but with a measured PG concentration of ≥ 70 mg/dL (≥ 3.9 mmol/L), will also be collected.

Certain categories of hypoglycemia will also be evaluated using a PG cutoff < 54 mg/dL (< 3.0 mmol/L) (International Hypoglycaemia Study Group 2017).

If a hypoglycemic event meets the criteria of severe, it needs to be recorded as serious on the AE CRF and reported to Lilly as an SAE.

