18. Removed hypoglycemia analyses for asymptomatic, nocturnal, and probable hypoglycemia events since they are already included in total hypoglycemia analyses, and added an additional hypoglycemia analysis, which will report all hypoglycemia events with PG <54 mg/dL, regardless of symptoms, and all severe hypoglycemia episodes for the ITT population, including events that occurred after patients started rescue therapy, since this was requested by FDA in other studies.
19. Clarified that subgroup analyses will be performed for the treatment regimen estimand only.
20. For baseline HbA1c ($\leq 8.0\%$, $>8.0\%$) subgroup analysis, added back the baseline HbA1c to the model as a covariate so that the results for actual and change from baseline are consistent, and the model terms are consistent within subgroup analyses.
21. Streamlined PRO section to reflect the latest user guide.
22. Removed the section specifying major cardiovascular events as an AE of interest since it was not included in the protocol as such, and the reporting of these events in this study population is unlikely. Any cardiovascular events that do occur should be reported as AEs and will be included in the analysis of TEAEs.
23. Updated the graphical testing scheme based on relevance of endpoints to clinicians and simulations using blinded data and published results from other trials.
24. Based on FDA feedback, the copy reference approach for multiple imputation for the primary analysis based on the treatment regimen estimand was changed to the washout method.
25. Based on FDA feedback, an interaction term of treatment by baseline insulin use was added to the negative binomial model for the analysis of hypoglycemia rates. In addition, the analyses for the incidence of hypoglycemia episodes and hypoglycemia rates will be conducted separately for the subsets of patients using insulin versus those not using insulin at baseline.

4. Study Objectives

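### On the reading that best fits the SAP, the total <54 mg/dL hypoglycemia category takes in symptomatic events that have no glucose reading

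*SAP*

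**What the plan says.** Protocol 10.4.1.2.1 defines a probable event as symptoms with no plasma glucose (PG) determination, "but that was presumably caused by a PG concentration of <70 mg/dL [<3.9 mmol/L". It adds that certain categories, which it does not name, will also be evaluated at a 54 mg/dL cutoff.

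SAP 5.15.2.1 keeps the condition that there is no reading but widens the presumption: the symptoms "are not accompanied by a PG determination (but that was presumably caused by a PG concentration of <70 or <54 mg/dL". Four further statements in that section matter:

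- Composition: "Total hypoglycemia includes any event that meets criteria for documented symptomatic, severe, asymptomatic, probable, or unspecified".
- Threshold rule: "Those categories that are defined by PG will be analyzed by the PG <70 and <54 mg/dL thresholds separately".
- Two versions of the total follow. The second is "Total Hypoglycemia (events with PG <54 mg/dL included".
- Reporting: "Incidence and rates for documented symptomatic, severe, and total hypoglycemia will be summarized for a 1-year (365-day) period". A negative binomial model is then specified for the rates, at both thresholds where they apply.

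The SAP revision history for Version 7 explains why probable events have no analysis of their own: "Removed hypoglycemia analyses for asymptomatic, nocturnal, and probable hypoglycemia events since they are already included in total hypoglycemia analyses".

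On a separate detail, the SAP defines relative hypoglycemia as symptoms "but with a measured PG concentration of >70 mg/dL (3.9 mmol/L", whereas Protocol 10.4.1.2.1 sets it at >=70 mg/dL.

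**The concern.** An event without a glucose value can reasonably be presumed hypoglycemic, which is what the protocol does. It cannot be assigned to the more serious <54 mg/dL band. If probable events pass into Total <54, that output mixes measured <54 events and severe events with symptomatic events whose glucose may have been 54 to 69 mg/dL, or not low at all. The <54 label would then be wrong for an unknown share of what is counted.

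The summary tables would not show this, because probable events are no longer reported separately; only the listing of individual episodes would reveal them. Hypoglycemia is a secondary safety objective (Protocol 6.2, SAP 4.2), and total hypoglycemia is one of the three categories that SAP 5.15.2.1 reports as incidence and rate.

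**Working it through.** The plan gives no figure to reproduce. The check applies the SAP rules in order and then asks what could be said about size.

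**Step 1. Which components are filtered by threshold?** The threshold rule covers categories defined by PG. Taking each component of total hypoglycemia in SAP 5.15.2.1:

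| Component | Has a PG value by definition? | Enters Total <70 | Enters Total <54 |
|---|---|---|---|
| Documented symptomatic | Yes | if <70 | if <54 |
| Asymptomatic | Yes | if <70 | if <54 |
| Unspecified (symptom data missing) | Yes | if <70 | if <54 |
| Severe | Not necessarily; qualifies on clinical grounds | all | all |
| Probable | No | all | all, since nothing filters or removes them |

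So, as written, Total <54 = measured <54 events + severe events + every probable event.

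**Step 2. Does another reading fit?** The label of the second total could be taken to require a measured value below 54. That reading has two difficulties. The added <54 in the SAP definition of probable events would then do nothing. Severe events without a reading would also drop out, although the SAP puts severe events in the total and accepts that a reading may be unavailable for them. The reading in Step 1 has neither difficulty.

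**Step 3. What does the rest of the SAP suggest?** The exploratory composites (SAP 4.3 and 5.16.1) list probable events beside documented symptomatic events at <70 only. That agrees with the protocol's presumption and not with the widened one.

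**Step 4. Size.** Let T be the number of Total <70 events, p the share of T that is probable, and q the share that is measured <54 or severe.

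- Total <54 as written = (p + q) × T
- Total <54 without probable events = q × T
- Relative excess = p/q

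The documents give neither p nor q. Purely as assumptions:

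| | q = 10% | q = 15% | q = 30% |
|---|---|---|---|
| p = 5% | 50% | 33% | 17% |
| p = 10% | 100% | 67% | 33% |
| p = 20% | 200% | 133% | 67% |

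As p approaches zero the excess vanishes whatever q is, and at p = 10%, q = 50% it is 20%. The table shows how the excess depends on the two shares and estimates neither. It concerns event counts; the proportion of patients with at least one event may change less, because a patient with both kinds of event is counted once either way. Total <70 is unaffected.

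**Step 5. Relative hypoglycemia.** A symptomatic reading of exactly 70 mg/dL is not documented symptomatic hypoglycemia (<70) in either document. It is relative hypoglycemia under the protocol (>=70) but falls in no category under the SAP (>70). The SAP keeps relative events out of the total and specifies no incidence or rate analysis for them, so no planned result changes.

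**The case against.** The strongest reply is that the inclusion is inferred. A reader might conclude that the SAP expressly counts probable events as <54. It does not: no sentence says so, the label of the second total can be read as requiring a value, and probable events are not given the explicit pair of <70 and <54 categories that documented, asymptomatic and nocturnal events receive. This stands as a limit on certainty. It does not remove the need for a rule, because two programmers could follow the same text and obtain different Total <54 counts.

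The second reply is that clean <54 information is already planned, and in part this stands. SAP 5.15.2.1 reports documented symptomatic events with its own <54 category. It also plans a separate analysis of all events with PG <54 plus all severe episodes, and a summary of measured <54 events on and off insulin. None is a full substitute. The first omits asymptomatic events. The second includes post-rescue events, which the primary hypoglycemia analysis censors. The third is descriptive, split by insulin use, and does not add severe events.

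The third reply is that few probable events may occur. Patients receive a glucometer and are told to test whenever symptoms suggest hypoglycemia (Protocol 7.1). That is a fair point, although the same section asks for the glucose value in the diary only if one is available.

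Finally, the protocol leaves open which categories are evaluated at 54 mg/dL, so having a <54 total is not itself a departure. Hypoglycemia also lies outside the hypotheses H1 to H12 that SAP 5.3 controls for multiplicity. Both points stand.

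**Conclusion.** The point holds as a defect of definition in a safety summary. SAP 5.15.2.1 departs from the protocol's presumption for probable events and, on the reading that best fits its text, admits events of unknown glucose to Total <54. The conclusion rests on that reading, which is the more coherent one but is not stated outright.

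The size is unknown and may be small. A reader might infer from the table above that the <54 count is inflated by a particular amount; both inputs are assumed, so no such figure is supported.

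A reader might also infer that the excess would differ by arm, because gastrointestinal reactions in adults were more frequent on dulaglutide (21.3% on placebo, 31.6% on 0.75 mg and 41.0% on 1.5 mg; Protocol 10.4.1.2.5) and might be mistaken for hypoglycemia. Nothing in the documents says that such symptoms would be recorded as probable hypoglycemia, so this remains conjecture.

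The primary and key secondary efficacy tests are not touched. The relative-hypoglycemia mismatch is real but editorial. A correction is worth making because the <54 label would otherwise be inaccurate under the rule as written, and the remedy is simple.

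**What to change.** In SAP 5.15.2.1, before the primary database lock:

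1. Restore the protocol wording for probable symptomatic hypoglycemia, so that the presumed cause is PG <70 mg/dL only.
2. Define Total <54 as documented symptomatic, asymptomatic and unspecified events with measured PG <54 mg/dL, plus all severe events whether or not a reading exists.
3. State that probable events count in Total <70 only.
4. As an editorial alignment, change relative hypoglycemia to PG >=70 mg/dL to match Protocol 10.4.1.2.1.

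The cost is a change of wording and one programming condition, with no new data. The one substantive loss is that a true <54 event that was neither measured nor severe no longer appears in Total <54; it stays in Total <70.
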